In the pooled analysis of KEYNOTE-28 and KEYNOTE-158 evaluating pembrolizumab as monotherapy in patients with advanced anal squamous cell carcinoma the ORR to pembrolizumab was 10.9% (15/137) (Marabelle A. *et al.*, 2020).

It has been acknowledged that combining immune checkpoint blockade with a HPV-antigen targeting immunotherapy can represent a complementary immune strategy to increase the proportion of patients benefiting from checkpoint blockers and promising results have been published. In a single arm trial evaluating ISA101, a synthetic long peptide HPV-16 vaccine targeting E6 and E7, in combination with nivolumab in patients with advanced HPV-16+ tumors, an ORR of 33% (8/24) has been observed (Massarelli E. *et al.*, 2019). MEDI0457, a DNA vaccine expressing HPV16/18 E6/E7 proteins and IL-12, was evaluated in combination with anti-PD-L1 durvalumab in patients with R/M HPV+ SCCHN. ORR was 22.2% (6/27) in

this study (Aggarwal C. *et al.*, 2020). The ORR of 23.5% observed in our study is in line with these published results.

The ultimate validation however whether adding a HPV vaccine to an anti-PD1/PD-L1 leads to an increase of the proportion of patients benefiting from checkpoint blockers needs to be done in a trial evaluating the combination of the vaccine with the anti-PD1/PD-L1 vs the anti-PD1/PD-L1 alone. This randomized phase II trial will include patients with any HPV-16 associated anogenital cancer stratified on the primary site (anal, cervix, genital).

1.3.8. Rationale for the restriction on the extent of liver metastases for eligibility in phase II part 2

Out of the 34 patients for the pooled efficacy analysis, 15 presented anal cancer, 8 oropharyngeal cancer, 6 cervical cancer and 5 vulvar/vaginal cancer. Median age was 61 years, the majority (88%) had received at least 1 prior line of chemotherapy (CT) with 32% having received \geq 2 lines.

8 patients achieved confirmed response according to RECIST 1.1 (1 CR, 7 PR, ORR 23.5%). Responses were observed in all primary tumor types and across all lines of prior therapy. Regarding the type of organs affected, there was a positive trend for lymph nodes; conversely the presence of liver metastases had a significant negative impact on outcome: ORR was 0% and PFS 1.4 months in patients with liver metastases (n=11) versus 34.8% and PFS of 5.6 months in patients without liver metastases (n=23).

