2 OBJECTIVES

2.1. Primary objective

Phase Ib: To evaluate the safety and tolerability of the combination of TG4001 plus avelumab in patients with recurrent or metastatic HPV-16 positive advanced malignancies.

Phase II part 1: To evaluate the efficacy of TG4001 combined to avelumab in terms of Overall Response Rate (ORR) by using RECIST 1.1 in patients with recurrent or metastatic (R/M) HPV-16 positive advanced malignancies including oropharyngeal SCCHN.

Phase II part 2: To compare the PFS of TG4001 in combination with avelumab vs avelumab alone in patients with R/M HPV-16 positive advanced malignancies and without liver metastases at baseline. PFS will be evaluated based on RECIST 1.1.

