6.4.2. Randomization

Non applicable for the phase Ib and the phase II part 1.

Randomization is applicable for the phase II part 2.

Upon satisfying all inclusion and exclusion criteria, the Investigator or his/her delegate will proceed to randomization which will be done in the eCRF.

- In patients without liver metastases at baseline randomization will be conducted equally in a 1:1 ratio TG4001 with avelumab (combination arm) versus avelumab alone (monotreatment arm). A stratification will be done on primary tumor site.
- In patients with liver metastases at baseline randomization will be conducted equally in a 1:1 ratio TG4001 with avelumab versus avelumab alone, no stratification will be performed.

The patient must start the study treatment according to allocation during randomization on the day of randomization (+1 day) if randomized into the combination arm and 1 week after randomization (+/- 1 day) if randomized into the monotreatment arm.

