Phase II part 1: Evaluable patients' population for tumor response (evaluable per protocol population, EPP): consists of all included patients who were dosed with both IMPs (TG4001 + avelumab) and have at least one baseline and one post-baseline evaluable CT-scan at week 6 after start of study treatment with a best overall response assessment different from 'Unknown' according to RECIST 1.1 evaluation criteria. However, if a patient progressed or died due to underlying cancer before scheduled scan 6 weeks after study treatment start could be performed, the patient will still be included in the evaluable population. Any patient who has a major inclusion/exclusion violation, major dosing violation, or major protocol conduct violation will be excluded from the EPP. Major dosing violation is considered when minimum exposure is not met defined as at least 6 TG4001 injections and 3 avelumab administrations except if patient has progressed or died due to underlying disease before or at the first evaluation. Due to potential abscopal effect when associating radiotherapy and immunotherapy, patients receiving palliative radiotherapy will be analyzed separately. Whatever the reason for withdrawal, except for disease progression and death due to underlying cancer before scheduled scan 6 weeks after study treatment start could be performed, patients considered as non-evaluable for tumor response will be replaced.

Phase II part 2: Full Set Analysis (FAS) will be the primary set for efficacy analyses. It consists of all randomized patients who were administered at least one dose of IMP(s) according to the treatment allocated at randomization.

Evaluable patients' population per protocol (evaluable per protocol population, EPP): consists of all patients from the FAS without any major inclusion/exclusion violation, major dosing violation as defined for phase II part 1, or major protocol conduct violation who were dosed with IMP(s) according to the treatment allocated at randomization and have at least one baseline and one post-baseline evaluable CT-scan at week 6 after start of study treatment with a best overall response assessment different from 'Unknown' according to RECIST 1.1 evaluation criteria.

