Phase II part 2: The primary endpoint of phase II part 2 is PFS by RECIST 1.1 criteria. The FAS will be the primary population for efficacy analyses in the phase II part 2. These analyses will be repeated on the EPP.

Progression Free Survival (PFS) is defined as the time from the date of randomization to the date of first documented tumor progression or death due to any cause, whichever occurs first. If a patient has not had a PFS event at the cut-off date for analysis or at the date when a further antineoplastic therapy (other than those planned as study treatment in the protocol) is started, PFS will be censored at the date of last evaluable tumor assessment before the cut-off or start of further antineoplastic therapy.

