10.4.2. Efficacy analyses

The analysis of the efficacy endpoints will be performed on the EPP and repeated on the SAF. The analysis of efficacy will be based on RECIST 1.1.

• Overall Response Rate (ORR)

Overall response rate (ORR) is defined as the proportion of patients whose best overall response is either CR or PR according to RECIST version 1.1. Proportions of patients with a best overall response of CR or PR will be presented along with exact 95% confidence intervals. Patients with best overall response ‘unknown’ will be summarized by reason for having unknown status. Phase II part 2: ORR will be compared between the 2 treatment arms using a (two-sided) 95% CI for the difference in proportion of patients whose best overall response is either CR or PR, stratified by indication using Cochran-Mantel-Haenszel Chi-Square test.

• Progression Free Survival (PFS)

Phase Ib and phase II part 1: PFS (in months) is defined as the time from the date of first study treatment administration to the date of first documented tumor progression or death due to any

cause, whichever occurs first. PFS will be censored if no progression or death is observed at the cut-off date for analysis, or at the date when a further antineoplastic therapy is started. The censoring date will be the date of the last evaluable tumor assessment before the cut-off date or start of further antineoplastic therapy.

Phase II part 2: PFS (in months) is defined as the time from the date of randomization to the date of first documented tumor progression or death due to any cause, whichever occurs first. PFS will be censored if no progression or death is observed at the cut-off date for analysis, or at the date when a further antineoplastic therapy is started. The censoring date will be the date of the last evaluable tumor assessment before the cut-off date or start of further antineoplastic therapy. The primary analysis will be a comparison of PFS between the 2 treatment arms using an unstratified log rank test at the one-sided 5% level in the FAS. A stratified log rank test stratified by indication will be also performed as supportive analysis. [REDACTED]

[REDACTED] HR (together with associated 95% CI) resulting from the stratified and unstratified Cox model will also be presented.

PFS will be presented descriptively using Kaplan-Meier curves. Summary statistics from the Kaplan-Meier distributions will be determined.

- **Duration of Overall Response (in case of CR or PR)**

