Duration of overall response in months (DoR) applies only to patients whose best overall response is CR or PR. The start date is the date of first documented response (CR or PR) and the end date is the date of event defined as first documented disease progression or death due to underlying cancer.

DoR will be censored if progression or death due to underlying cancer is not observed at the cut-off date for the analysis or start of further antineoplastic therapy. The censoring date will be the date of the last evaluable tumor assessment. Kaplan-Meier curves of DoR will be constructed. Summary statistics from the Kaplan-Meier distributions will be determined.

- **Disease Control Rate (DCR)**

Disease control rate (DCR) is defined as the proportion of patients whose best overall response is either CR, PR, or stable disease (SD).

- **Overall Survival (OS)**

Phase Ib and phase II part 1: OS is defined as the time from the date of first study treatment administration to the date of death due to any cause. If a patient is not known to have died, survival will be censored at the date of last contact.

Phase II part 2: OS is defined as the time from the date of randomization to the date of death due to any cause. If a patient is not known to have died, survival will be censored at the date of last contact. OS will be presented descriptively using Kaplan-Meier curves. Summary statistics from the Kaplan-Meier distributions will be determined. OS will be compared between the 2 treatment arms using an unstratified log rank test and log-rank stratified by indication at the one-sided 5% level in the FAS. [REDACTED]

[REDACTED] HR (together with associated 95% CI) resulting from the stratified and unstratified Cox model will also be presented.

- **Phase II part 2: Percentage of patients with liver metastases at baseline who have disease progression at D43**

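### The part 2 analysis-set and primary-test wording does not carry the restriction to patients without liver metastases that the primary objective and the design impose

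*Combined protocol and SAP*

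**What the plan says.** Section 2.1 states the part 2 primary objective as a PFS comparison "in patients with R/M HPV-16 positive advanced malignancies and without liver metastases at baseline". The synopsis and section 10.2 repeat it.

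Part 2 randomises two cohorts. Patients without liver metastases are randomised 1:1, stratified by primary tumour site. Section 6.4.2 adds a second, unstratified randomisation: "In patients with liver metastases at baseline randomization will be conducted equally in a 1:1 ratio TG4001 with avelumab versus avelumab alone".

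The part 2 FAS appears in the synopsis, the definitions table and section 10.1, each time without reference to liver metastases. Section 10.1 reads: "It consists of all randomized patients who were administered at least one dose of IMP(s) according to the treatment allocated at randomization". Section 10.3.1 says: "The FAS will be the primary population for efficacy analyses in the phase II part 2". Section 10.4.2 describes the primary analysis as a "comparison of PFS between the 2 treatment arms using an unstratified log rank test at the one-sided 5% level in the FAS", with a supportive log-rank test stratified by indication.

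For the secondary endpoints, section 10.4.2 says "OS will be compared between the 2 treatment arms using an unstratified log rank test and log-rank stratified by indication", again in the FAS, and stratifies the ORR comparison by indication. Neither sentence names a cohort.

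The design text is specific. The synopsis and sections 3.1.2, 3.2 and 10.2 attach the PFS hypotheses, the 37-event interim, the final event requirement (at least 69 in section 3.2) and the 80 or 120 patients to the cohort without liver metastases. The liver cohort has its own secondary endpoint, progression at D43.

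**The concern.** The objective names one population and the sentence defining the primary test names another, wider one. A programmer working from 10.1 and 10.4.2 alone would pool two separately randomised cohorts in an unstratified test.

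The FAS cannot simply be read as silently excluding the liver cohort. The part 2 analysis sets are the SAF, the FAS and an EPP drawn from the FAS, so excluding that cohort from the FAS would leave the D43 endpoint without an efficacy set. Section 10.5 also uses the FAS for part 2 disposition, baseline and treatment tables, by arm and not by cohort. What is missing is a stated primary-analysis subset.

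Liver status matters for outcome in the protocol's own data. Section 1.3.8 gives PFS of 1.4 months and ORR of 0% with liver metastases (n=11), against 5.6 months and 34.8% without (n=23). No readable part 2 between-arm analysis adjusts for it.

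The trial is open label, and sections 3.1.2 and 3.2 already reflect the interim result. The primary population should not be left to be settled after the final data are seen.

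**Working it through.** **1. The plan's own event number.** Section 10.2 states 76 events for 95% power at one-sided 5%; its favourable-zone rule uses 74. The medians are 4.5 and 2.0 months (section 3.2), so HR = 2.0/4.5 = 0.444. Freedman's formula gives

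d = (z₀.₉₅ + z₀.₉₅)² × [(1 + HR)/(1 − HR)]² = (1.645 + 1.645)² × (1.444/0.556)² = 10.82 × 6.76 = 73.2, so 74.

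This equals the 74 and is within 2 of the 76. At 69 events the same approximation gives power Φ(√69 × 0.556/1.444 − 1.645) = Φ(1.55) = 94%. The calculation belongs to the cohort without liver metastases and has no term for anyone else.

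**2. What literal pooling would do.** Inputs:
- 80 patients without liver metastases, 1:1, exponential PFS with medians 4.5 and 2.0 months, accrued at 2 per month (section 3.2).
- Final analysis at 69 events counted in that cohort, as the synopsis and sections 3.1.2 and 3.2 indicate.
- Assumed: 10, 20 or 30 liver-cohort patients, because the planned number is blacked out.
- Assumed: no effect in the liver cohort, with median PFS 1.4 months in both arms, or 2.0 months as a sensitivity case.
- Unstratified one-sided 5% log-rank test, HR estimated as exp[(O − E)/V], 10,000 simulated trials per row, with no interim look, dropout or sample-size change.

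| Liver patients added | Median in liver cohort | Mean events in test | Median HR | Power |
|---|---|---|---|---|
| 0 | – | 69 | 0.43 | 95% |
| 10 | 1.4 / 2.0 | 78 / 78 | 0.47 / 0.47 | 94% / 94% |
| 20 | 1.4 / 2.0 | 87 / 87 | 0.50 / 0.50 | 93% / 92% |
| 30 | 1.4 / 2.0 | 97 / 96 | 0.53 / 0.53 | 91% / 90% |

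Accrual at 3 per month changes no power figure by more than about 1 percentage point.

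**3. Hand check of the dilution.** Weight the log HR by events, with zero effect in the liver cohort. Using the unrounded 0.425 for the no-liver HR, 69 × ln(0.425) = −59.0. Dividing by 78.2, 87.4 and 96.5 events gives −0.755, −0.676 and −0.612, or HRs of 0.47, 0.51 and 0.54. These agree with the simulation to within 0.01.

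**4. OS and ORR.** No arithmetic is needed. Section 6.4.2 creates two randomisations. Section 10.4.2 stratifies by indication, and no readable sentence separates or stratifies by the cohort in which a patient was randomised.

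**The case against.** The strongest reply is that no reader of the whole protocol could mistake the population. The objective names it. The synopsis specifies the medians, the log-rank test and the 37-event look for that cohort, and section 10.2 puts the PFS comparison under a heading for it. Primary tumour site is a randomisation stratum only in that cohort, which suits the supportive test stratified by indication. On this view the FAS sentence governs dosing and allocation, and the objective supplies the population. This stands as evidence of intent. It does not make the test sentences complete.

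A reader might infer that the 69-event trigger would be used up by liver-cohort events. In the same simulation that would lower power to about 91%, 86% and 80% for 10, 20 and 30 patients with a 1.4-month median. The documents do not support that reading, because they attach the event counts to patients without liver metastases.

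The 1.4-month figure is also open to challenge. It comes from 11 patients on the combination, 10 of whom had hepatic target disease above 30 mm (section 1.3.8), which part 2 excludes. The protocol's pessimism concerns extensive hepatic disease, and limited hepatic disease was admitted on purpose. Using 2.0 months changes little. The zero effect, however, is an assumption made here and not a statement in the protocol; some benefit in that cohort would reduce the dilution.

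The secondary objectives for ORR, OS, DoR and DCR are not limited to patients without liver metastases, so pooling them contradicts no stated objective. What remains is that the pooled ORR and OS comparisons ignore cohort.

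Finally, text after the PFS and OS test descriptions in 10.4.2 is blacked out, and the adaptive details are deferred to the SAP. A restriction could sit there. The visible primary-test sentence is nevertheless complete and names only the FAS.

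**Conclusion.** The inconsistency is real and should be corrected before the final analysis. The FAS, primary-endpoint and primary-test sentences cover all randomised and dosed part 2 patients, while the objective and the cohort-specific design cover only those without liver metastases.

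A reader might conclude that the sponsor plans a pooled primary test, or that the reported result cannot answer the stated question. The documents do not go that far: the intended population is clear, and harm arises only if the FAS wording is followed literally.

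In that case, with events still counted in the cohort without liver metastases, the median HR moves from about 0.43 to 0.47-0.53 and power from about 95% to between 90% and 94%. The power loss is modest; the diluted HR and the changed population matter more. These figures rest on an assumed 10 to 30 liver-cohort patients, no effect in them, and a fixed design without the interim adaptation.

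**What to change.** In sections 10.1, 10.3.1 and 10.4.2, the synopsis and the definitions table, state that:
- the primary PFS analysis, its repeat in the EPP, and the 37- and 69-event counts use FAS patients without liver metastases at baseline;
- the D43 progression endpoint uses FAS patients with liver metastases at baseline.

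Report the between-arm ORR and OS comparisons by cohort, or stratify any pooled comparison by liver-metastases cohort. Do not describe these secondary comparisons as confirmatory; the protocol does not.

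If the blacked-out text or the SAP already contains the restriction, the change is to bring these sections into line with it. The cost is a few sentences, with no new data, patients or assessments.

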Evaluable patients' population (evaluable per protocol population, EPP): consists of all patients from the FAS without any major inclusion/exclusion violation, major dosing violation as defined for phase II part 1, or major protocol conduct violation who were dosed with IMP(s) according to the treatment allocated at randomization and have at least one baseline and one post-baseline evaluable CT-scan at week 6 after start of study treatment with a best overall response assessment different from 'Unknown' according to RECIST 1.1 evaluation criteria.

Sample size:

Phase Ib of the study: there will be no formal sample size for the phase Ib of the study. The dose escalation part of the trial follows the methodology of a 3+3 cohort design for dose-finding studies in oncology. Depending on the observed DLTs, a maximum of 12 evaluable patients will be included in this part of the study.

Phase II part 1: a Simon's two-stage design will be used. The null hypothesis for response rate H_0 is set at 10% corresponding to the response rate observed in second line patients, the alternative hypothesis of efficacy is set at $H_A=25\%$, the type I error α is set at 5% one sided, the type II error β is set at 20% (power=80%). Under these hypotheses and applying a minimax two-stage Simon design, enough patients will be treated to obtain 22 evaluable patients as a first stage. If at least 3/22 patients are considered responders, the enrolment will be continued, otherwise it will be stopped. In the initial design and at the second stage enough patients should have been treated to obtain at least 40 evaluable patients in total. The study would have been considered positive with at least 8/40 responders. With a hierarchical strategy on the final analysis, a subgroup analysis performed in oropharyngeal SCCHN patients and with a null hypothesis for response rate (H_0) set at 10% and the alternative hypothesis of efficacy set at $H_A = 35\%$, 18 oropharyngeal SCCHN patients would have been needed to reach a power of 81% and actual alpha at 2.8%. This analysis would have been considered positive with at least 5 responders among the 18 SCCHN patients. The second stage of the Simon's design has not been done following the decision to exclude oropharyngeal SCCHN and to change to a randomized controlled two-arms study (phase II part 2).

Phase II part 2:

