Evaluable patients	
Evaluable patients for DLT determination: patients must complete the first 4 weeks of the combination or discontinue before the end of the 4 weeks for a DLT. Patients must receive at least one dose of both IMPs (TG4001 + avelumab) and have at least one valid post-baseline safety assessment.
 
Patients who are not evaluable for phase Ib safety analysis or are withdrawn for other reasons than toxicity, will be replaced.
 
Phase II part 1: Evaluable patients population for tumor response: patients who were dosed with both IMPs (TG4001 + avelumab) and have at least one baseline and one post-baseline evaluable CT-scan at week 6 after start of study treatment with a best overall response assessment different from 'Unknown' according to RECIST 1.1 evaluation criteria and have no major protocol violations or major dosing violations. Major dosing violation is considered when minimum exposure is not met, defined as at least 6 TG4001 injections and 3 avelumab administrations except if patient has progressed or died due to underlying disease before or at the first evaluation.
 
Phase II part 2: Full Analysis Set (FAS) which consists of all randomized patients who were administered at least one dose of IMP(s) according to the treatment allocated at randomization.

Start of study treatment	Corresponds to date of Day 1 for phase Ib and phase II part 1 and to date of randomization for phase II part 2
--------------------------	--

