6 TREATMENT PLAN

6.1. Trial medication administrations

The study treatments for all patients in the phase Ib and the phase II part 1 of the study are TG4001 with avelumab.

For the phase II part 2, study treatments are TG4001 with avelumab in the combination arm and avelumab alone in the monotherapy arm.

The study drugs treatment will be given on an outpatient setting, where all facilities for observation of the patients during and after study drug administrations are available and are in accordance with the local regulations laws.

[figure not shown]

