7.3. During the study treatment period

The time windows allowed for the visits are:

- +/- 1 day from Day 1 to Day 36
- - 3/+1 days for the further study treatment visits beyond Day 36

Tumor evaluation must be performed every 6 weeks for the first 9 months after treatment start and every 12 weeks thereafter, with a time window allowed of +/- 7 days.

12-leads ECG during treatment period as clinically indicated.

In case of potential symptoms of myocarditis / pericarditis during study treatment (such as chest pain, shortness of breath, heart palpitations, and reduced tolerance to exercise), cardiac laboratory analyses (e.g. creatinine kinase-myocardial band, troponin), ECG and echocardiography (or MUGA scan) will be requested. If abnormal findings indicate possible myo- or pericarditis, the patient will be referred to consulting a cardiologist.

From Day 1 to Day 36

- Physical examination* including vital signs and body weight on Days 1, 8, 15, 22, 29, 36

- Performance status* on Days 1, 15, 29
- Adverse events reporting on Days 1, 8, 15, 22, 29, 36
- Concomitant medications and non-drug therapies collection on Days 1, 8, 15, 22, 29, 36
- Hematology* on Days 1 (not for phase II part 2), 8, 15, 22, 29, and 36
- Biochemistry*, creatinine* on Days 1 (not for phase II part 2), 8, 15, 22, 29, and 36
- TSH on Day 36*
- Blood pregnancy test* for women of childbearing potential on Day 36
- Type I and II HLA on Day 1* (not for phase II part 2)
- Blood sample collection for immunomonitoring* on Days 1, 8 and D15 (D15 for phase II part 2 only); on Day 1, 6 hours post-dose for patients randomized in the combination arm and treated with TG4001 (for phase II part 2 only)
- Inclusion/exclusion criteria check on Day 1
- Randomization on Day 1 for phase II part 2
- TG4001 SC administration once a week on Days 1, 8, 15, 22, 29, and 36 (phase Ib, phase II part 1 and phase II part 2 combination arm)
- Avelumab IV administration once every 2 weeks starting on Day 8 (D22 and D36) for all patients

Beyond Day 36 up to Month 6, Day 204

- Physical examination* including vital signs, body weight and performance status every 2 weeks
- Adverse events reporting every 2 weeks
- Concomitant medications and non-drug therapies collection every 2 weeks
- Hematology* every 2 weeks
- Biochemistry*, creatinine* every 2 weeks
- TSH* every 6 weeks
- Blood pregnancy test* for women of childbearing potential every 6 weeks

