8 ASSESSMENT OF EFFICACY

- Assessment of efficacy according to RECIST VERSION 1.1

The assessment of efficacy is based on Response Evaluation Criteria in Solid Tumors (RECIST) version 1.1 (Eisenhauer E.A. *et al.*, 2009).

For efficacy evaluation, patients must have at least one measurable lesion by CT/MRI scan (minimum size not less than 10 mm) at baseline and a post-baseline evaluable CT-scan at week 6 after start of study treatment with a best overall response assessment different from 'Unknown' according to RECIST evaluation criteria. However, if a patient progressed or died due to underlying cancer before scheduled scan 6 weeks after study treatment start could be performed, the patient will still be included in the evaluable population.

Tumor assessment will be performed LOCALLY according to investigator's assessment every 6 weeks from the start of study treatment until disease progression or for a period of 9 months after start of study treatment, whichever occurs first. Beyond 9 months after start of study treatment, the evaluations will be performed every 12 weeks until disease progression. The same schedule of tumor evaluation will be applied for patients who stopped the study treatment for any reason other than progressive disease.

For all patients, tumor response assessment will be performed by preferably CT (or MRI) of the head and neck, chest, abdomen and all other known sites of disease (e.g. pelvis, if applicable) and other established assessments of tumor burden if CT/MRI imaging is insufficient for the individual patient. In case of bone pain, an adequate radiological and/or isotopical exploration is to be performed to research metastases. All the scans performed at baseline and other imaging performed as clinically required (other supportive imaging) need to be repeated at subsequent visits.

Per RECIST, the imaging method used at baseline should be matched at all subsequent assessments, but, for a number of reasons such as site error (e.g. switch from MRI to CT) or renal dysfunction (making contrast a risk), this will not always be done. A strict implementation of RECIST would mean that any change in imaging method compared to one used at baseline should lead to unknown overall response at given assessment. However, a change in the use of contrast does not necessarily represent a change in precision since for many tumor types, the assessment can be done despite the fact that contrast has changed.

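### The part 2 per-protocol set inherits a 6-injection TG4001 minimum that no avelumab-alone patient can meet, so as written it drops every control who is progression-free at the first scan

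*Combined protocol and SAP*

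**What the plan says.** For phase II part 2, Section 10.1 makes the FAS the primary efficacy set. It then defines the EPP as FAS patients "without any major inclusion/exclusion violation, major dosing violation as defined for phase II part 1, or major protocol conduct violation" who were also dosed as allocated and have a baseline scan and an evaluable week-6 scan. The synopsis has the same cross-reference: "major dosing violation as defined for phase II part 1, or major protocol conduct violation".

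The definition referred to is in the part 1 paragraph of Section 10.1. The minimum exposure there is "at least 6 TG4001 injections and 3 avelumab administrations except if patient has progressed or died due to underlying disease" by the first evaluation.

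Section 6.1 describes the part 2 arms: "study treatments are TG4001 with avelumab in the combination arm and avelumab alone in the monotherapy arm". Section 10.3.1 says the part 2 efficacy analyses will be repeated on the EPP. Section 10.6 leaves the deviations that determine the EPP to the SAP and plans a data review meeting before the final analysis. Nowhere do the documents give a part 2 minimum exposure by arm.

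**The concern.** The minimum was written for a single-arm study in which everyone received both products. Carried unchanged into a two-arm comparison, it asks control patients for injections they are never scheduled to receive. The only way a control can stay in the EPP is through the exception, that is, by progressing or dying of the disease by the first evaluation.

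The exclusion is therefore one-sided and depends on outcome. Fully dosed combination patients stay in whatever happens to them, while controls stay in only if they fail early. A repeat PFS analysis on that set is biased towards the combination. If ORR and DCR were also repeated on it, the retained controls could not have a response or stable disease, so both control rates would be zero by construction.

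**Working it through.** **1. Where the 6 + 3 minimum comes from.** Section 7.3 gives "TG4001 SC administration once a week on Days 1, 8, 15, 22, 29, and 36" for patients allocated TG4001, and "Avelumab IV administration once every 2 weeks starting on Day 8 (D22 and D36) for all patients". The first post-baseline scan is on Day 43. Doses scheduled before it:

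| | TG4001 | Avelumab |
|---|---|---|
| Combination arm | 6 (D1, 8, 15, 22, 29, 36) | 3 (D8, 22, 36) |
| Avelumab-alone arm | 0 | 3 (D8, 22, 36) |
| Part 1 minimum | 6 | 3 |

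The minimum is exactly the combination schedule up to the first scan. A fully compliant control has 0 of the 6 required injections. All controls who are progression-free at the first scan are therefore excluded. This follows from the wording alone and needs no model.

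**2. How many controls that is.** Inputs: control median PFS 2.0 months and 40 patients per arm (Section 10.2 and synopsis); Day 43 is 42 days after Day 1. Assumptions: exponential PFS, and the Section 8 allowance for progression or cancer death before the week-6 scan is applied.

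Time to scan = 42 / 30.4375 = 1.38 months. Share progression-free S = 2^(−1.38 / median).

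| Control median (months) | S | Excluded of 40 | Kept of 40 |
|---|---|---|---|
| 1.5 (assumed) | 0.529 | 21.1 | 18.9 |
| 2.0 (protocol) | 0.620 | 24.8 | 15.2 |
| 2.5 (assumed) | 0.682 | 27.3 | 12.7 |
| 3.0 (assumed) | 0.727 | 29.1 | 10.9 |

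Across the ±7-day scan window at a 2.0-month median, S runs from 0.671 (day 35, 26.9 excluded) to 0.572 (day 49, 22.9 excluded). With 60 per arm, from the 120 patients in Section 3.1.2, 60 × 0.620 = 37.2 are excluded and 22.8 kept. Without the Section 8 allowance, the kept numbers are smaller still.

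**3. Effect on the repeat log-rank test.** Simulation: 2,000 trials, 40 per arm, exponential PFS with a 2.0-month median in both arms (no true effect), no dropout, combination arm fully compliant, controls kept only if the event falls by day 42. Share of trials with one-sided z > 1.645 in favour of the combination:

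| Event dating | FAS | EPP as written | Median z, EPP |
|---|---|---|---|
| 6-weekly scans | 5.8% | 100% | 4.1 |
| Exact dates | 4.6% | 100% | 4.7 |

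The mean number of controls kept was 15.2 (5th to 95th percentile 10 to 21 with scan dating). A separate run of 5,000 trials with exact dates and the cut at 43 days gave 5.5% in the full set and 100% in the EPP. With both medians at 4.5 months it gave 5.2% and 99.8%.

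**4. Neighbouring wording.**
- The part 2 EPP paragraph requires a week-6 scan but does not repeat the allowance that Section 8 states generally ("However, if a patient progressed or died due to underlying cancer before scheduled scan 6 weeks after study treatment start could be performed", the patient still counts as evaluable).
- The Definitions table equates part 2 evaluable patients with the FAS, whereas Section 10.1 uses the term for the EPP.
- The opening sentence of Section 10.4.2 (EPP, repeated on the safety set) fits part 1 but names no phase. Sections 10.1 and 10.3.1 already give FAS then EPP for part 2.

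**The case against.** The strongest reply is that nobody intended this reading. Part 1 requires dosing with both products; the part 2 EPP changes that to dosing as allocated, so the authors did adapt the set to two arms. The Definitions table attaches the 6 + 3 minimum to part 1 only. Section 10.6 leaves room to settle the rule in the SAP and at the data review meeting, where labelling every progression-free control a violator would be hard to miss. No primary, interim or sample-size decision uses the EPP.

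Most of that stands as a limit on the consequence. It does not remove the defect. Dosing as allocated is a further condition for entry; it does not alter the minimum imported by cross-reference. The protocol already fixes that minimum, so a sensible SAP rule would contradict Section 10.1. The trial is open label, and deciding EPP membership at a late review meeting would mean doing so with allocation and outcome visible.

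Three points about size are also fair. The simulation result follows almost by construction once controls are kept only for early events; the patient counts carry the message. Applying the Section 8 allowance while reading the injection count literally mixes two readings, though dropping the allowance only leaves fewer controls. Sections 3.1.2 and 3.2 now expect at least 80 patients because of slow accrual, so 40 per arm is the more relevant illustration than 60. The glossary and 10.4.2 items are editorial and do not carry the point.

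**Conclusion.** The concern holds: followed exactly, the part 2 EPP rule removes all controls who are progression-free at the first scan and keeps only early failures. The complete exclusion rests on the text alone. The 62% figure (53% to 73% for control medians of 1.5 to 3.0 months) rests on exponential PFS and on the Section 8 allowance being applied. The consequence is confined to the supportive EPP repeat and arises only if the definition is carried into the analysis unchanged, so it is minor. In that case the repeat could not serve as a check on the FAS result.

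**What to change.** - In Section 10.1 and the synopsis, mirrored in the SAP, define the part 2 minimum exposure by allocated arm: TG4001 count for the combination arm only, avelumab count for both arms. A fully dosed control who is progression-free at the first scan then stays in.
- Carry the Section 8 allowance for progression or cancer death before the week-6 scan into the part 2 EPP definition.
- Align the Definitions table entry for part 2 evaluable patients with Section 10.1.
- Limit the opening sentence of Section 10.4.2 to phase Ib and phase II part 1, and state FAS repeated on the EPP for part 2.

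The cost is a few sentences, with no extra data and no effect on patients. The change should be made before EPP membership is determined.
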